# 4.2.2 Secondary Endpoints

- ORR, and DR, according to RECIST Version 1.1 as determined by investigator review, and OS
- invPFS, ORR, DR, and OS in patients with baseline T790M mutations confirmed by central EGFR mutation assay
- Change from baseline in QOL as measured using the PRO of EORTC QLQ-C30, EORTC QLQ-LC13, the DLQI, and the EQ-5D following treatment with CO-1686 versus erlotinib
- Treatment-emergent AEs, laboratory abnormalities and ECG abnormalities
- Plasma PK parameters for CO-1686 based on sparse sampling

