# 10.5 Clinical Laboratory Assessments as Adverse Events and Serious Adverse Events

It is the responsibility of the investigator to assess the clinical significance of all abnormal values as defined by the list of reference ranges from the local laboratory. In some cases, significant changes in laboratory values within the normal range will require similar judgment.

An abnormal laboratory value that is not already associated with an AE is to be recorded as an AE only if any one of the following criteria is met:

- An action on the study drug is made as a result of the abnormality
- Intervention for management of the abnormality is required
- At the discretion of the investigator should the abnormality be deemed clinically significant

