#### 11.2 Statistical Methods

#### 11.2.1 General Considerations

Quantitative variables will be summarized using descriptive statistics (N, mean, standard deviation, median, minimum, and maximum) and/or frequency and percentages for medically relevant categories. Categorical variables will be presented using frequencies and percentages.

Kaplan-Meier methodology will be used to summarize time-to-event variables. The number of patients with events and the number of censored patients will also be presented. The stratified logrank test will be used to compare the time-to-event distributions between the randomized treatment groups. The same variables used to stratify the randomization will be used in the stratified analyses. In addition, the Cox proportional hazards model will be used to estimate the HR between the randomized treatment groups.

The Fisher's Exact Test will be used to compare frequencies between treatment groups and the t-test will be used for comparing means between treatment groups.

All data will be used to their maximum possible extent but without any imputations for missing data. Results from Phase 2 and Phase 3 will be presented separately and pooled.

All statistical analyses will be conducted with the statistical analysis software (SAS®) system, Version 9.1 or higher.

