## 11.2.5.3 Clinical Laboratory Evaluations

Clinical laboratory evaluations include the continuous variables for hematology, serum chemistry, and urinalysis. Laboratory values will be presented in International System of Units. The baseline laboratory value will be defined as the last value prior to or on the day of the first dose of CO-1686 or erlotinib, but prior to receiving study drug. The on-treatment period will be defined as the day after the first dose of CO-1686 or erlotinib to 28 days after the last dose of CO-1686 or erlotinib. Laboratory values collected during the on-treatment period will be included in the summary tables. The laboratory values collected after the on-treatment period will only be presented in the data listings.

The summary of laboratory data will include descriptive statistics (N, mean, standard deviation, minimum, median, and maximum) of the maximum, minimum, and last value during the treatment period by dose group and study phase. Summaries using descriptive statistics of the change from baseline to the maximum, minimum, and last value during the on-treatment period will also be given by dose group and study phase. Separate listings will be produced for clinically significant laboratory abnormalities (i.e., those that meet Grade 3 or 4 criteria according to CTCAE) by dose group.

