Appendix D, Table 2. Hyperglycemia Lab-shift by Acetylator Status

	Overall (N = 635)		
			Rapid (n = 76)
Subjects with any post-baseline glucose values > 250 mg/dL	121 (40%)	65 (25%)	17 (22%)
Subjects with 2 or more post- baseline glucose values > 250 mg/dL	51 (17%)	36 (14%)	7 (9%)
Subjects with any post-baseline glucose values > 500 mg/dL	11 (4%)	7 (3%)	1 (1%)
Subjects with 2 or more post- baseline glucose values > 500 mg/dL	3 (1%)	0 (0.0)	0 (0.0)

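### Laboratory abnormalities are a secondary endpoint, but no table of patients by laboratory CTCAE grade and arm is specified, and glucose is sampled unequally between arms

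*Combined protocol and SAP*

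**What the plan says.** Section 4.2.2 lists as one secondary endpoint "Treatment-emergent AEs, laboratory abnormalities and ECG abnormalities".

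For laboratory values, Section 11.2.5.3 plans three things:
- for the values themselves, "descriptive statistics (N, mean, standard deviation, minimum, median, and maximum) of the maximum, minimum, and last value during the treatment period by dose group", with a further split by phase of the study;
- for change, "Summaries using descriptive statistics of the change from baseline to the maximum, minimum, and last value during the on-treatment period", divided in the same way;
- for severe values, line listings: "Separate listings will be produced for clinically significant laboratory abnormalities (i.e., those that meet Grade 3 or 4 criteria according to CTCAE".

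Three other places bear on the point:
- Section 11.2.1 lets quantitative variables be summarized by descriptive statistics "and/or frequency and percentages for medically relevant categories". The Safety Analysis paragraph of the synopsis says in general terms that laboratory information will be tabulated.
- Section 11.2.5.2 plans numbers and percentages of patients with AEs by CTCAE grade, and a separate table of Grade 3 or greater AEs.
- Section 10.5 governs when a laboratory value enters those tables: "An abnormal laboratory value that is not already associated with an AE is to be recorded as an AE only if any one of the" three conditions listed there is met. The conditions are action on study drug, a need for intervention, or the investigator's judgment of clinical significance.

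**The concern.** An abnormality is a yes-or-no or graded outcome, so its natural summary is the proportion of patients affected. The laboratory section describes the distribution of extremes and lists the severe values, but does not commit to that proportion. Section 11.2.5.5 does commit to it for the ECG half of the same endpoint line: maximum QTcF is put into categories, with the number and percentage of patients in each.

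The synopsis names hyperglycemia as the most common toxicity of CO-1686. If the plan is followed to the letter, the only by-arm rate of severe hyperglycemia comes from AE reports. The one by-arm laboratory summary that reflects severity, the maximum, is taken over more visits in one arm than in the other.

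**Working it through.** The plan states no figure on this point, so there is none to reproduce. The check compares the text and then does three small calculations.

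**1. What is committed to**

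| Item | Number and % by category or grade? | Section |
|---|---|---|
| QTcF | Yes, required | 11.2.5.5 |
| AEs, including hyperglycemia recorded as an AE | Yes, required, by grade | 11.2.5.2 |
| Laboratory values in general | Permitted (and/or); no test, grade or cut-off named | 11.2.1 |
| Laboratory values, specific plan | Not specified; listings for Grade 3/4 | 11.2.5.3 |

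A laboratory table is feasible. Section 9.6.1.1 has laboratory abnormalities graded by CTCAE and recorded on the eCRF, and Section 11.2.5.3 defines the baseline value that a grade shift needs.

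**2. Do the planned statistics recover the rate?** The mean and SD do not. The documents give no distribution of maximum glucose, so the means and SDs below are assumptions. The last two columns show P(maximum > 250 mg/dL).
- Normal: 1 − Φ((250 − m)/s).
- Lognormal: σ² = ln(1 + (s/m)²), μ = ln m − σ²/2, P = 1 − Φ((ln 250 − μ)/σ).

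| Assumed mean/SD (mg/dL) | Normal | Lognormal |
|---|---|---|
| 180/60 | 12.2% | 12.0% |
| 200/80 | 26.6% | 22.0% |
| 200/120 | 33.8% | 24.8% |

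The gap runs from 0.2 to 9.0 percentage points. The planned median and range narrow the possibilities but do not fix the proportion either.

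**3. AE counts and laboratory counts in Appendix D.** Table 1 gives Grade 3 or greater hyperglycemia AEs (combined terms). Table 2 gives "Subjects with any post-baseline glucose values > 250 mg/dL". Both cover the same 635 patients on CO-1686.

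| Acetylator group | AE | Laboratory |
|---|---|---|
| Slow (300) | 131 (43.7%) | 121 (40.3%) |
| Intermediate (259) | 66 (25.5%) | 65 (25.1%) |
| Rapid (76) | 13 (17.1%) | 17 (22.4%) |
| All (635) | 210 (33.1%) | 203 (32.0%) |

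The totals nearly agree. The group differences (AE minus laboratory) are +10, +1 and −4, so they change direction. Only totals are given, so how many patients are counted in both tables is unknown.

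**4. Glucose visits by arm (Table 9-1 and its footnote on fasting glucose).** Scheduled post-baseline visits through Cycle 3 Day 1:
- CO-1686: C1D4, C1D8, C1D15, C2D1, C2D15, C3D1 = 6.
- Erlotinib: C2D1, C3D1 = 2.

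A maximum, a worst grade or a count of patients with any high value over 6 visits has more chances to find an abnormality than one over 2. Unrestricted comparisons therefore favor detection on CO-1686. The first common visit is Day 28 ± 3 after C1D1, so 25 days at the earliest. Section 7.4.1 says that hyperglycemia generally appears within the first 3 weeks (21 days). The common visits start at least 25 − 21 = 4 days after that window.

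**The case against.** The strongest reply is that the plan offers more than a quick reading suggests. All of the following stands:
- A reader might infer that only means are planned. Medians, SDs, ranges and change from baseline are planned too.
- A reader might infer that laboratory grades will never be tabulated. Section 11.2.1 allows it, so the accurate statement is that no such table is specified.
- The AE tables will give a rate of severe hyperglycemia by group. On CO-1686 that rate is less discretionary than it may seem. The hyperglycemia guidance in Section 7.4.1 calls for intervention at high fasting glucose, and a need for intervention alone meets Section 10.5. Section 9.6.1.2 also has clinically significant laboratory abnormalities documented as AEs.
- Appendix D is weak evidence. It sets combined-term AE grades against a glucose cut-off that the documents do not equate with Grade 3. It pools doses from 500 to 1000 mg BID and has no erlotinib arm. The slow-to-rapid ratio is 43.7/17.1 = 2.6 by AE and 40.3/22.4 = 1.8 by laboratory value, which is tempting to cite, but it leans on 4 of 76 rapid acetylators (13 v 17). AE counts exceed laboratory counts overall, so the totals show no under-reporting.
- Development has stopped and Appendix D closes enrollment. This is descriptive safety reporting, and no efficacy conclusion depends on it.

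The reply does not remove the gap. A permission in Section 11.2.1 is not a commitment, and the AE tables are a different source, filtered by investigators who know the treatment. Section 13.9 still calls for a clinical study report.

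**Conclusion.** The concern holds in a limited form and is minor. A named secondary endpoint has no specified table of patients by laboratory grade and arm. The planned by-arm summary of maximum glucose rests on 6 v 2 scheduled post-baseline visits through Cycle 3 Day 1.

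The effect on the trial's results cannot be sized from the documents. Appendix D shows only that AE and laboratory counts need not match (210 v 203 of 635 overall, with differences in both directions by group). A reader might infer from it that AE reporting will distort the comparison with erlotinib. The documents do not support that, because there is no erlotinib group, the two measures are not equivalent and patient-level agreement is unknown.

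The visit counts assume that Table 9-1 was followed in the early cycles. Unscheduled tests could widen or narrow the imbalance.

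**What to change.** Keep the Grade 3/4 listings and add to Section 11.2.5.3:

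- By randomized treatment, the number and percentage of patients by worst on-treatment CTCAE grade, and the shift from baseline grade, for each gradable hematology and chemistry parameter.
- For glucose, every between-arm comparison (worst grade, shift, maximum, and counts above the Appendix D Table 2 thresholds) based on visits scheduled in both arms.
- For glucose on CO-1686, the same results over all visits, shown descriptively.

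Give the thresholds in SI units, as Section 11.2.5.3 requires. Section 7.4.1 sets 250 mg/dL equal to 13.87 mmol/L, so 500 mg/dL is 2 × 13.87 = 27.74 mmol/L.

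The cost is small: SAP wording and a few tables from data already collected. The real limitation is that the common-visit comparison leaves out C1D4 to C1D15, when most hyperglycemia is expected, so some early episodes may have resolved by the first common visit. The all-visit CO-1686 table is there to show that period, and the report should say that it has no erlotinib counterpart. Only analysis wording changes; monitoring and clinical management stay as they are.

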#### 11.2.5.4 Vital Sign Measurements

The baseline vital sign measurement will be defined as the last value prior to or on the day of the first dose of CO-1686 or erlotinib. The on-treatment period will be defined as the day after the first dose of CO-1686 or erlotinib to 28 days after the last dose of protocol-specified treatment. Vital sign measurements collected during the on-treatment period will be included in the

summary tables. The vital sign measurements collected after the on-treatment period will only be presented in the data listings.

The summary of vital sign data will include descriptive statistics (N, mean, standard deviation, minimum, median, and maximum) of the maximum, minimum, and last value during the on-treatment period by dose group and study phase. Summaries using descriptive statistics of the change from baseline to the maximum, minimum, and last value during the on-treatment period will also be given by dose group.

#### 11.2.5.5 12-lead Electrocardiograms

ECG intervals will be stratified into categories indicative of potential clinical significance. Each patient's maximum QTcF intervals from the pretreatment visit and treatment period visits will be classified as  $\leq 450$  ms, > 450 to  $\leq 480$  ms, > 480 to  $\leq 500$  ms, and > 500 ms. For each patient's maximum change from the pretreatment ECG visit for QTc, intervals will be classified into < 30 ms,  $\geq 30$  to < 60 ms, and  $\geq 60$  ms. The number and percentage of patients in each classified category will be presented. Additional endpoints will include abnormal T waves and U waves and other ECG intervals and diagnostic parameters.

Descriptive statistics will be used to summarize other ECG parameters of PR, QRS, QT, and RR interval, and the corresponding changes from pretreatment ECG visit at each time point. Plots of the mean QT/QTc over time for C1D1 and End-of-Treatment/pretreatment ECG day measurements will be provided.

## 11.2.5.6 Other Safety Measurements

Body weight and ECOG performance status will be summarized with descriptive statistics (N, mean, standard deviation, median, minimum, and maximum). Concomitant medications/procedures will be tabulated and summarized.

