#### **Safety Analysis**

Data from all patients who receive 1 or more doses of CO-1686 or erlotinib will be included in the safety analyses. AEs, clinical laboratory information, vital signs, ECOG performance status, body weight, and concomitant medications/procedures will be tabulated and summarized.

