## 9.6.1.3 Vital Signs

Vital signs will include blood pressure, pulse, and body temperature. All vital signs will be obtained after the patient has been resting for at least 5 min. Vital signs will be performed at screening and at each study visit, including the End-of-Treatment Visit.

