## 9.6.1.5 Body Weight and Height

Height will be measured only during the screening visit of the main part of the study. Weight will be measured at all study visits (the patient should be in light indoor clothes).

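### Section 11.2.5.6 summarises body weight without change from baseline and ordinal ECOG status as a continuous score, although both baselines are collected

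*Combined protocol and SAP*

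**What the plan says.** The operative sentence, in Section 11.2.5.6 (Other Safety Measurements), is "Body weight and ECOG performance status will be summarized with descriptive statistics (N, mean, standard deviation, median, minimum, and maximum"). It gives no baseline definition, on-treatment window, visit, change, shift or category. The synopsis (Safety Analysis) adds only that "ECOG performance status, body weight, and concomitant medications/procedures will be tabulated and summarized".

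Elsewhere the plan does more:

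- Vital signs (Section 11.2.5.4) have a defined baseline and on-treatment period, and a summary of "change from baseline to the maximum, minimum, and last value during the on-treatment period".
- Laboratory values (Section 11.2.5.3) are handled in the same way. ECGs (Section 11.2.5.5) get change from pretreatment and QTcF categories.
- The general rule in Section 11.2.1 is "Categorical variables will be presented using frequencies and percentages". For quantitative variables it also allows descriptive statistics "and/or frequency and percentages for medically relevant categories".

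The vital-sign rule does not reach weight. Section 9.6.1.3 states "Vital signs will include blood pressure, pulse, and body temperature", and weight has its own Section 9.6.1.5.

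The data exist. Section 9.6.1.5 says "Weight will be measured at all study visits". Section 9.6.1.7 and Table 9-1 place ECOG at screening, C1D1, Day 1 of each later cycle and End-of-Treatment. Inclusion criterion 6 limits entry to ECOG 0 or 1.

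**The concern.** ECOG status is an ordered 0-5 scale (Appendix B). A mean and SD treat its steps as equal and do not say how many patients sit at each level. Because entry requires 0 or 1, a later score of 2 or more is a decline, and it is easy to count. Section 11.2.5.6 asks for no such count.

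For weight, a summary of the measured value mixes differences between patients with what happened to each patient. Section 11.2.5.6 does not use the baseline that would separate the two.

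Comparative safety and tolerability is a secondary objective (Section 4.1.2), and both measures are listed safety assessments in the synopsis. Table 3-2 reports treatment-related nausea in 28.4%, decreased appetite in 12.2% and vomiting in 12.2% of patients on CO-1686, and Section 3 associates erlotinib with diarrhea. What is at stake is how clearly the safety tables show weight loss and functional decline by arm.

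**Working it through.** There is no plan figure to reproduce; the check is a comparison of sections plus two illustrations.

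**Side by side.** Change from baseline is planned for laboratory values, vital signs and ECGs, and for neither weight nor ECOG. Frequencies are required for categorical variables in Section 11.2.1, but Section 11.2.5.6 gives ECOG a mean and SD.

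**Illustration 1: ECOG (assumed counts, N = 100 each).**

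| Score | 0 | 1 | 2 | 3 |
|---|---|---|---|---|
| Group A | 24 | 59 | 0 | 17 |
| Group B | 40 | 11 | 48 | 1 |

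- Sum: A = 59 + 0 + 51 = 110; B = 11 + 96 + 3 = 110. Both means are 1.10.
- Sum of squares: A = 59 + 0 + 153 = 212; B = 11 + 192 + 9 = 212. Both SDs are sqrt((212 - 110²/100)/99) = sqrt(91/99) = 0.96.
- Median: the 50th and 51st ordered values are 1 in both groups (cumulative counts 24, 83 in A and 40, 51 in B).
- Minimum 0 and maximum 3 in both.
- Share at 2 or more: A = 0 + 17 = 17%; B = 48 + 1 = 49%.

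All six planned statistics agree, yet the share with poor status differs almost threefold.

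**Illustration 2: weight (assumed values; the documents give none).**

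If a fraction f of an arm loses 10% of body weight, the arm mean falls by f × 0.10 × mean weight.

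- f = 0.10: 0.6 kg (mean 60, SD 10), which is 0.06 SD; 0.7 kg (mean 70, SD 15), which is 0.05 SD.
- f = 0.30: 1.8 kg, which is 0.18 SD; 2.1 kg, which is 0.14 SD.

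Precision of an arm difference: 95% half-width = 1.96 × SD × sqrt(2/n per arm), with assumed SD 12-16 kg for measured weight and 3-5 kg for within-patient change.

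| n per arm | Measured weight | Change from baseline |
|---|---|---|
| 100 (Phase 2) | 3.3-4.4 kg | 0.8-1.4 kg |
| 500 (Phase 3 cap) | 1.5-2.0 kg | 0.4-0.6 kg |

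Under these assumptions, between-patient spread makes the comparison roughly two to five times less precise (12/5 = 2.4; 16/3 = 5.3).

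**The case against.** A reader might infer three stronger things, and the documents do not support them.

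- *That only raw means are reported.* SD, median, minimum and maximum are listed too, and the ECOG maximum shows the worst score. Section 11.2.5.6 is silent on change from baseline; it does not rule it out.
- *That the plan has no categories for these measures.* That is true of Section 11.2.5.6 alone. Section 11.2.1 requires frequencies for categorical variables and permits medically relevant categories for quantitative ones. For ECOG the accurate point is that the specific section does not match the general rule.
- *That weight loss and decline would be hidden.* Section 10.1 counts any unfavourable sign or symptom as an adverse event, and Section 11.2.5.2 tabulates events by term and CTCAE grade. Section 11.2.4.2 summarises the EORTC scales by visit and analyses time to a 10-point symptom worsening.

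A simpler ECOG example also fails. If 30% worsen by one level or 10% by three, the mean rises by 0.30 either way (0.30 × 1 = 0.10 × 3). But from an entry score of 0 or 1, and with no other decline, the first gives a maximum of at most 2 and the second at least 3, so the listed maximum separates them. The matched pair in the working avoids this. It was found by searching for agreement, so it shows that the ambiguity is possible, not that it is likely.

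Power is not the right yardstick for a descriptive summary. On the assumed SDs, Phi(2/(SD × sqrt(2/n)) - 1.96) for a 2 kg difference in measured weight is 14-22% at 100 per arm but 51-75% at 500, so the smaller size alone would mislead.

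Finally, development has stopped, no more patients will be enrolled (Appendix D), and Appendix D Table 4 keeps weight but does not list ECOG. The benefit is mainly to the reporting of data already collected.

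These points narrow the concern. None of them supplies a planned change from baseline for weight or an ECOG shift summary.

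**Conclusion.** The point holds as a minor one. Section 11.2.5.6 plans no change from baseline for weight and treats an ordinal score as continuous, out of line with Sections 11.2.5.3 to 11.2.5.5 and with Section 11.2.1, although both baselines are collected. The listed statistics cannot show the share of patients who decline: 17% and 49% at ECOG 2 or more can look identical. That example is exact arithmetic on assumed counts. The weight figures depend on assumed means and SDs and show direction and rough size only. The effect is confined to descriptive safety reporting; the primary analysis, its error rate and trial conduct are untouched.

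**What to change.** Amend Section 11.2.5.6 to adopt the baseline and on-treatment definitions of Section 11.2.5.4, and by arm:

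- summarise weight as change and percent change from baseline, with n (%) losing at least 5% and at least 10%;
- summarise ECOG as n (%) per score, with a shift table from baseline to worst on-treatment score and n (%) reaching 2 or more.

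The on-treatment window in Section 11.2.5.4 runs to 28 days after the last dose of protocol-specified treatment, and Section 9.4 counts crossover treatment as such. The tables should therefore state how values after crossover are handled for Phase 2 erlotinib patients. They should also note that ECOG covers data collected before the Extension Phase.

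The cost is a few lines of wording and two standard tables, with no new data collection.
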